### 6.5.2. Management of Hyperphosphatemia

Hyperphosphatemia is an expected on-target pharmacologic effect of FGFR inhibition. Hyperphosphatemia should be managed with diet modifications, phosphate binders and diuretics, or a dose reduction per the recommendations in [Table 8](#).

The use of diet modifications alone include food exchanges from high-phosphate foods to low-phosphate foods and can be implemented once serum phosphate levels are above the ULN but do not exceed 7.0 mg/dL. Diet modification should continue with the inclusion of phosphate binders once serum phosphate levels exceed 7.0 mg/dL. Examples of phosphate binders are sevelamer HCl (examples of name brands: Renegel® and Renvela®) or lanthanum HCl. Administration of phosphate binders should be 3 times per day (eg, with each meal) to reduce absorption of phosphate. Doses and frequency of doses should be based on the participant's tolerance for the binder and the control of the serum phosphate. If binders are used to manage hyperphosphatemia during treatment, it is recommended to stop binders, together with the low-phosphate diet, at the same time pemigatinib is stopped to reduce the risk of hypophosphatemia.

Note that CTCAE v5.0 now has a category for grading hyperphosphatemia.

**Table 8: Recommended Approach for Hyperphosphatemia Management**

Serum Phosphate Level	Supportive Care	Guidance for Interruption/Discontinuation of Pemigatinib	Guidance for Restarting Pemigatinib
> 5.5 mg/dL and ≤ 7 mg/dL	Initiate a low-phosphate diet.	No action.	Not applicable.
> 7 mg/dL and ≤ 10 mg/dL	Initiate/continue a low-phosphate diet and initiate phosphate-binding therapy. Monitor serum phosphate approximately twice a week, and adjust the dose of binders as needed; continue to monitor serum phosphate at least twice a week until level returns to ≤ 7 mg/dL.	If serum phosphate level continues to be > 7 mg/dL and ≤ 10 mg/dL with concomitant phosphate-binding therapy for 2 weeks, or if there is recurrence of serum phosphate level in this range, interrupt pemigatinib for up to 2 weeks.	Restart at the same dose when serum phosphate is < 7 mg/dL. If serum phosphate level recurs at > 7 mg/dL, restart pemigatinib with dose reduction.
> 10 mg/dL	Continue to maintain a low-phosphate diet, adjust phosphate-binding therapy, and start/continue phosphaturic agent. Continue to monitor serum phosphate approximately twice a week until level returns to ≤ 7 mg/dL.	If serum phosphate level is > 10 mg/dL for 1 week following phosphate-binding therapy and low-phosphate diet, interrupt pemigatinib. If there is recurrence of serum phosphate level in this range following 2 dose reductions, permanently discontinue pemigatinib.	Restart pemigatinib at reduced dose with phosphate binders when serum phosphate is < 7 mg/dL.

### **6.5.3. Criteria for Permanent Discontinuation of Study Drug**

The occurrence of unacceptable toxicity not caused by the underlying disease will require that the study drug be permanently discontinued. Unacceptable toxicity is defined as follows:

- The occurrence of an AE that is related to study drug that, in the judgment of the investigator or the sponsor's medical monitor, compromises the participant's ability to continue study-specific procedures or is considered to not be in the participant's best interest.
- An AE requiring more than 3 dose reductions.
- A persistent AE requiring a delay of therapy for more than 2 weeks (14 days) unless a greater delay has been approved by the sponsor.

See Section 7 for discontinuation procedures.

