## 6.5. Dose Modifications

Individual decision regarding dose modifications of pemigatinib should be made using clinical judgment and in consultation with the sponsor's medical monitor, taking into account relatedness of the AE to the study treatment and the participant's underlying condition. Adverse events that have a clear alternative explanation or transient ( $\leq$  72 hours) abnormal laboratory values without associated clinically significant signs or symptoms, may be exempt from dose-reduction rules.

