### 6.5.1. Criteria and Procedures for Dose Interruptions and Adjustments of Study Drug

Safety concerns should be discussed with the sponsor immediately upon occurrence or awareness to determine if the participant should continue or discontinue study treatment.

Treatment with pemigatinib may be delayed up to 2 weeks (14 days) to allow for resolution of toxicity. Participants may resume treatment if no medical condition or other circumstance exists that, in the opinion of the investigator, would make the participant unsuitable for further participation in the study. The treating investigator should contact the sponsor to discuss the case of any participant whose treatment has been delayed for more than 14 days before restarting treatment with pemigatinib. See [Table 7](#) for guidelines.

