**Table 7: Guidelines for Interruption and Restarting of Study Drug**

Adverse Event	Action Taken
Chemistry	

AST and/or ALT is <math>> 5.0 \times</math> ULN.

 
Note: In participants with liver metastasis-related elevations at baseline, contact sponsor to discuss clinical management and possible dose reductions.
	
Step 1: Interrupt pemigatinib up to 2 weeks (14 days) until the toxicity has resolved to <math>\leq</math> Grade 1 except by approval of the medical monitor.
 
Step 2: Restart pemigatinib at same dose. If assessed as related to pemigatinib, restart pemigatinib at the next lower dose; monitor as clinically indicated. If AE persists for more than 1 cycle, consider a dose reduction.

Other toxicities	

Retinal pigment epithelium detachment

	
Step 1: If RPE detachment is noted on an OCT examination, remain on study drug and follow up with OCT re-examination in 2 weeks.
 
Step 2: If RPE detachment is noted on re-examination, reduce dose of pemigatinib and re-examine via OCT in 2 weeks.
 
Step 3: If RPE detachment is not resolving on re-examination after dose reduction, further reduction of pemigatinib or dose hold until resolution of RPE detachment

Any Grade 1 or Grade 2 toxicity.

	Continue pemigatinib treatment and treat the toxicity; monitor as clinically indicated.

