**Table 7: Guidelines for Interruption and Restarting of Study Drug (Continued)**

Adverse Event	Action Taken
• Recurrent Grade 2 toxicity	Step 1: Interrupt pemigatinib up to 2 weeks (14 days), until toxicity resolves to $\leq$ Grade 1 Step 2: If related to pemigatinib, restart pemigatinib at the next lower dose level. Monitor as clinically indicated and if AE persists, consider further dose reduction.
• Any Grade 3 toxicity	Step 1: Interrupt pemigatinib up to 2 weeks (14 days), until toxicity resolves to $\leq$ Grade 1. Step 2: Restart pemigatinib at same dose. If assessed as related to pemigatinib, restart pemigatinib at the next lower dose; monitor as clinically indicated. If AE persists for more than 1 cycle, consider a dose reduction.
• Any recurrent Grade 3 toxicity after 2 dose reductions.	Discontinue pemigatinib administration and follow-up per Protocol. (Exceptions require approval of sponsor.)
• Any other Grade 4 toxicity. • QT/QTc to $>$ 500 ms or to $>$ 60 ms over baseline.	Discontinue pemigatinib administration and follow-up per Protocol.

For participants who present with possible or confirmed SRD/RPED based on OCT, the guidelines in [Table 7](#) should be followed. It is recommended to discuss the findings with the sponsor's medical monitor before making changes to the participant's treatment.

Per CTCAE v 5.0, retinal detachment is graded as 3 (macular sparing) and 4 (macula-off), but this refers to rhegmatogenous retinal detachment (when a hole occurs in the retina). There is no grading for SRD/RPED (no hole in the macula, just fluid accumulation). Therefore, grading should be based on the CTCAE v5.0 term of retinopathy.

The starting dose of pemigatinib will be 13.5 mg QD, intermittent dosing regimen (2 weeks on treatment and 1 week off treatment). Dose reductions should follow as noted below:

- Starting dose: 13.5 mg QD intermittent dosing
- First dose reduction: 9 mg QD intermittent dosing
- Second dose reduction: 4.5 mg QD intermittent dosing

Dose reductions below 4.5mg QD are not allowed. Following a dose reduction and resolution of pemigatinib-related toxicities, a participant's dose may be returned to the starting dose at the discretion of the investigator and in consultation with the sponsor's medical monitor.

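### The stop at a fourth dose reduction in Protocol 6.5.3 does not fit a dose ladder with two reductions, and the counting rule is not stated

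*Protocol*

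**What the plan says.** **The stopping rule.** Protocol Section 6.5.3 requires permanent discontinuation for unacceptable toxicity and defines that term in three ways. The first is a judgment by the investigator or medical monitor about a related AE. The second is a count: "An AE requiring more than 3 dose reductions". The third is a persistent AE that delays therapy beyond 14 days, unless the sponsor has approved a longer delay. Section 7.1.1 lists unacceptable toxicity under Section 6.5 among the reasons for which treatment must stop.

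**The ladder.** Section 6.5.1, below Table 7, starts at 13.5 mg, makes 9 mg the first reduction, and ends with "Second dose reduction: 4.5 mg QD intermittent dosing". It adds: "Dose reductions below 4.5mg QD are not allowed". After toxicity resolves, the dose may go back to the starting dose at the investigator's discretion, in consultation with the medical monitor. No limit on such returns is given.

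**Other counts.** Table 7 stops treatment for a Grade 3 toxicity that recurs once two reductions have been made, with exceptions by sponsor approval. Table 8 does the same for phosphate above 10 mg/dL that recurs after two reductions.

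**Rows that lower the dose.** Six rows of Tables 7 and 8 do so. The AST/ALT and Grade 3 rows of Table 7 use the same words: "If assessed as related to pemigatinib, restart pemigatinib at the next lower dose; monitor as clinically indicated". For retinal pigment epithelium (RPE) detachment, Step 2 reads "If RPE detachment is noted on re-examination, reduce dose of pemigatinib and re-examine via OCT in 2 weeks", and Step 3 offers "further reduction of pemigatinib or dose hold until resolution of RPE detachment". Section 6.6.1, on moderate CYP3A4 inhibitors, does state an exception for a participant already at 4.5 mg.

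**Judgment.** Section 6.5 says that individual dose decisions "should be made using clinical judgment and in consultation with the sponsor's medical monitor". Section 6.5.1 sends safety concerns to the sponsor at once "to determine if the participant should continue or discontinue study treatment".

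**The concern.** A mandatory stop should be something a site can apply from the dosing record. Here the number is larger than the number of reductions the ladder contains. A participant who goes straight down the ladder and stays at the floor cannot reach it through reductions actually made. For a participant who was returned to 13.5 mg, two sites could read the same dose history differently. One would add the reductions before and after the return. The other would start again at zero. Only the first would stop treatment under this criterion.

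The gap matters most in rows that tell the site to go one level lower, carry no stop of their own, and do not say what applies at 4.5 mg. There the count in 6.5.3 is the only numeric limit on repeated reductions. Participant safety and uniform conduct across sites are at stake. The efficacy estimate is not.

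**Working it through.** **1. Threshold.** More than 3, for a whole number, means 4 or more.

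**2. One pass down the ladder.** There are three levels (13.5, 9 and 4.5 mg), so a pass contains at most 3 − 1 = 2 reductions. Since 2 < 4, the criterion is not met. A direct step from 13.5 to 4.5 mg would use up the ladder with a count of 1.

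**3. With returns to 13.5 mg.** With R returns there are R + 1 passes, so at most 2 × (R + 1) reductions can be made. Requiring 2 × (R + 1) ≥ 4 gives R ≥ 1.

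| Dose history (AE-driven reductions made) | Cumulative count | Meets 4 or more? |
|---|---|---|
| No return | 2 | No |
| One return, from 9 mg | 1 + 2 = 3 | No |
| One return, from 4.5 mg | 2 + 2 = 4 | Yes, if cumulative |
| Two returns, both from 9 mg | 1 + 1 + 2 = 4 | Yes, if cumulative |

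If the count resets at each return, the maximum stays at 2 and the criterion is never met. Neither document says which applies. SAP Section 6.3 lists participants with a reduction or interruption and defines no count.

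**4. Reading *requiring* to include reductions that cannot be made.** At 4.5 mg a further reduction may be called for but is barred. If such occasions count, with no return, one gives 2 + 1 = 3 (not met) and two give 2 + 2 = 4 (met). No passage states this reading.

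**5. Per AE or overall.** The criterion speaks of a single AE. If the count is per AE, two different AEs with one reduction each exhaust the ladder with counts of 1 and 1. If it is overall, the count is 2. Neither reaches 4.

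**6. CYP3A4-inhibitor reductions (Section 6.6.1).** These are one-level and reversible, and no AE calls for them. Adding them to the possible moves leaves the AE-driven result unchanged: at least one return to 13.5 mg is still needed for 4. Only if they are themselves counted can a total of 4 be reached without a return to 13.5 mg. For example, one AE reduction to 9 mg can be followed by three inhibitor-related reductions from 9 to 4.5 mg, with the dose going back to 9 mg after the first and the second: 1 + 3 = 4.

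**7. The six rows, read at the 4.5 mg floor.** On a single pass, two reductions made one level at a time mean 4.5 mg. A stop after two reductions is therefore a floor rule for that event.

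| Row | Stop or hold tied to the floor | What stays open at 4.5 mg |
|---|---|---|
| Table 7, AST/ALT, related | None | The whole row |
| Table 7, recurrent Grade 2, related | None | The whole row |
| Table 8, phosphate > 7 to 10 mg/dL, on recurrence | None | The whole row |
| Table 7, RPE detachment | Step 3 allows a hold | Step 2 only |
| Table 7, Grade 3, related | Next row stops on recurrence after two reductions | A first event in a participant already at 4.5 mg |
| Table 8, phosphate > 10 mg/dL | Same row stops on recurrence after two reductions | A first event in a participant already at 4.5 mg |

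Three rows are fully silent, and three are open only in part.

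**The case against.** The best defense is that 6.5.3 is an outer backstop. The count can be reached through the return that Section 6.5.1 permits, and earlier stops sit in front of it: the two-reduction stops in Tables 7 and 8, the 14-day limit, and the judgment criterion. Table 7 is presented as guidelines and Table 8 as a recommended approach, while Sections 6.5 and 6.5.1 route individual cases to the medical monitor or sponsor. The natural reading of the criterion is a running total for one AE, and nothing mentions a reset.

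Much of this stands. It disposes of three stronger readings that a reader might infer:

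- *The rule can never be met.* Not supported. With a cumulative count, one return from 4.5 mg is enough, and so are two barred reductions if those count.
- *Section 6.5.3 conflicts with the two-reduction stops in Tables 7 and 8.* Not supported. Those stops are specific to an event, and a site can follow them together with a later general stop. They are relevant because they use the number of steps the ladder has, and 6.5.3 does not.
- *Every row that lowers the dose is silent at 4.5 mg, so a participant there has no route to stopping.* Not supported. Three of the six rows have a stop or a hold for at least part of the situation, and the judgment and delay provisions apply throughout.

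What the defense does not do is make the number fit. The count is a separate criterion, so it should work without help from the other two. A running total is a plausible reading, but it is not written down, and even on that reading a participant who was never returned cannot exceed 2 reductions made.

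**Conclusion.** The point holds at low weight. On reductions actually made for an AE, the ladder gives 2 and the mandatory stop needs 4. Reaching it takes at least one return to 13.5 mg and a cumulative count that neither document defines. Three table rows also have no stop or hold tied to the floor, and three more are open in part.

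The result rests on three readings: that the count means reductions made, that only AE-driven reductions count, and that the dose moves only as Sections 6.5.1 and 6.6.1 allow. If barred reductions count, no return is needed and the stop falls on the second such occasion.

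The safety effect is limited by the judgment provisions and the 14-day criterion. The practical effect is minor: SAP Section 10.1 records that enrollment was terminated with fewer than 10 participants. Sample size and the ORR analysis are untouched. A reader might infer that the number in 6.5.3 is a slip for the number in the tables. The documents do not show which number was intended.

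**What to change.** The sponsor should reconcile Sections 6.5.1 (with Table 7), 6.5.2 (Table 8), 6.5.3 and 7.1.1 so that the count in 6.5.3 fits the dose ladder. The revised text should state:

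- whether reductions are counted per AE or over all AEs;
- whether the count carries over after a return to the starting dose, both for 6.5.3 and for the two-reduction stops in Tables 7 and 8;
- whether a reduction that is called for but unavailable at 4.5 mg counts;
- what applies at 4.5 mg in the three silent rows (AST/ALT, recurrent Grade 2, phosphate > 7 to 10 mg/dL), in RPE Step 2, and for a first Grade 3 event or a first phosphate value above 10 mg/dL in a participant already at that dose.

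The clinical team chooses the rule; none is proposed here. The cost is protocol wording or a clarification letter, with no effect on data collection, sample size or analysis.

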## **6.6. Concomitant Medications and Procedures**

All concomitant medications and treatments (including over-the-counter or prescription medicines, vitamins, vaccines, and/or herbal supplements) must be recorded in the eCRF. Any prior medication received up to 30 days before the first dose of study drug through 30 to 35 days after the last dose of study drug, or until the participant begins a new anticancer therapy, whichever occurs first, will be recorded in the eCRF. Any addition, deletion, or change in the dose of these medications will also be recorded. Concomitant medications administered for treatment of SAEs (as defined in Section 9.2) should be recorded even if the SAE is reported beyond 30 to 35 days after the last dose of study drug. Concomitant treatments/procedures that are required to manage a participant's medical condition during the study will also be recorded in the eCRF. The medical monitor should be contacted if there are any questions regarding concomitant or prior therapy.

### **6.6.1. Restricted Medications and Procedures**

The use of mild CYP3A4 inhibitors or inducers, moderate CYP3A4 inhibitors, proton pump inhibitors, and OCT2 substrates should involve careful monitoring. If the use of moderate CYP3A4 inhibitors is unavoidable, the pemigatinib dose should be reduced by one level (unless at 4.5mg). Once concomitant use of moderate CYP3A4 inhibitor is discontinued, as well as 3 half-lives of the CYP inhibitor, the dose of pemigatinib may be returned to the original dose.

Calcium-based, phosphate-binding medications should not be used due to a concern for soft tissue mineralization.

Palliative radiotherapy is permitted if considered of benefit and medically necessary by the investigator. The sponsor must be notified prior to start of any procedure that may be considered restricted.

## **6.6.2. Prohibited Medications and Procedures**

The following medications and measures are prohibited:

- The concomitant administration of potent CYP3A4 inhibitors and inducers and moderate CYP3A4 inducers (see [Appendix F](#)). Based on the low overall bioavailability of topical ketoconazole, there are no restrictions on topical ketoconazole.
- Any concomitant use of a selective FGFR inhibitor (other than the study drug).
- Any other investigational study drug for any indication.
- Use of any anticancer medications, treatments, or procedures other than the study drug. Discuss with the sponsor any treatment plans.

The sponsor must be notified prior to start of any procedure that may be considered prohibited.

## **6.7. Treatment After the End of the Study**

Upon completion of this study, for participants who are continuing to receive study drug and benefiting from treatment with pemigatinib, the rollover study, INCB 54828-801, is available.

## 7. DISCONTINUATION OF STUDY TREATMENT AND PARTICIPANT WITHDRAWAL

### 7.1. Discontinuation of Study Treatment

#### 7.1.1. Reasons for Discontinuation

Participants **must** be discontinued from study treatment for the following reasons:

- The participant is confirmed to be pregnant.
- Consent is withdrawn.

Note: Study staff must differentiate if the participant is withdrawing consent for the entire study or just continuing treatment. Withdrawing consent for the study will mean that the participant has explicitly indicated that they do not want to be followed any longer; in this case no further data, except data in public domain, may be solicited from or collected on the participant. If a participant chooses to withdraw consent for continuing treatment, this participant will remain on the study and will be followed for progression and survival.

- Further treatment would be injurious to the participant's health or well-being, in the investigator's medical judgment. The participant would still be followed for progression and survival.
- The study is terminated by the sponsor.
- The study is terminated by the local health authority, IRB, or IEC.
- Unacceptable toxicity has occurred, as noted in Section [6.5](#).
- Disease progression has been reported by the ICR.
- Other antineoplastic treatment (not including palliative radiation) is initiated.

A participant **may** be discontinued from study treatment as follows:

- If, during the course of the study, a participant is found not to have met eligibility criteria but is receiving clinical benefit as per the investigator, the medical monitor, in collaboration with the investigator, will determine whether the participant should be discontinued from treatment. This includes cases where the local genomic testing result is positive for an acceptable FGFR alteration (see [Appendix B](#)) but the central genomic testing is not.
- If a participant is noncompliant with study procedures or study drug administration in the investigator's opinion, the sponsor should be consulted for instruction on handling the participant.

#### 7.1.2. Discontinuation Procedures

In the event that the decision is made to permanently discontinue the study treatment, the EOT visit should be conducted. Reasonable efforts should be made to have the participant return for a follow-up visit. These visits are described in [Table 3](#). The last date of the last dose of study drug and the reason for discontinuation of study drug will be recorded in the eCRF.

### If a participant is discontinued from study treatment:

- The study monitor or sponsor must be notified.
- The reason(s) for discontinuation must be documented in the participant's medical record and the primary reason for discontinuation must be included in the eCRF.
- The EOT visit should be performed and date recorded.
- The status of the participant should be updated to EOT in the IRT.
- Participants must be followed for safety until the time of the follow-up visit or until study drug-related toxicities resolve, return to baseline, or are deemed irreversible, whichever is longest.

If the participant discontinues study treatment and actively withdraws consent for collection of follow-up data (safety follow-up or disease assessment), then no additional data collection should occur; however, participants will have the option of withdrawing consent for study treatment but continuing in the follow-up period of the study for safety/efficacy assessments.

